## **12.0 Data Management**

All data will be stored in the Redcap database as well as in paper documentation. Information about the participant (including their identifiable private information) may have all their identifiers removed and used for future research studies or distributed to other researchers for future research without additional informed consent. After participation, RedCAP data will be downloaded in excel format to the secure MUSC server. Paper documentation will be stored in locked cabinet within a locked office of the study team. In terms of publication, data will be published in aggregate form, so individual participants will not be identifiable in the final manuscript. No identifying information will be published.

Neuroimaging data will be collected from the 3T MRI scanner at [name]. All imaging data will be automatically transferred to and stored on a password-protected, encrypted secure server that limits data access to personnel directly involved with the study. The data will be analyzed using standard imaging analysis software packages such as FSL and SPM.

**Confidentiality and Quality Control:** All study personnel will complete Social-Behavioral-Educational research CITI training, and also complete in-lab training regarding data security practices. Study personnel will be trained in the IRB protocol. The investigator, and co-investigators will be available to monitor data collection to ensure quality, confidentiality, and adherence to the IRB protocol.

The study's procedures will take place at the MUSC [name] Neuroimaging. Regarding documentation, participant names will appear only on the IRB-approved Consent and HIPAA. Patients will be receiving tFUS within the MRI scanner and they will be aware of this information prior to choosing to participate.

## **13.0 Provisions to Monitor the Data to Ensure the Safety of Subjects**

There are three areas in which safeguards to protect subjects from undue risk require discussion. These include: (1) procedures used to obtain informed consent, (2) procedures used to ensure confidentiality of the subject data, and (3) procedures used to minimize possible risks associated with the laboratory procedures. Regarding informed consent, participants are fully advised on the research procedures to be used, the amount of time required of them, the possible risks and benefits of the procedures, their right to refuse participation in the study without prejudice, their right to terminate participation at any moment without prejudice, and the name and telephone number of the principal investigator. All subjects will be required to have capacity to consent. Regarding confidentiality, subjects are informed that the information they provide will be kept strictly confidential, with access limited to the research staff. Participation in the study will be treated as confidential, as will all records. The identity of subjects will be protected with alphanumeric codes. All data will be kept in locked file cabinets or on secure servers designed for use and access by study team only.

We do not anticipate any adverse events to occur in this study, however the experienced research team has a long-standing record of recording and reporting unanticipated adverse events to the IRB. We will report any adverse event within 48 hours to the IRB.

## 14.0 Withdrawal of Subjects

Participants will be informed during consenting that they are free to withdraw from the study at any time. They will be informed that they are not obligated to participate once the study is initiated and in particular will be reminded prior to tFUS stimulation and neuroimaging that they may discontinue stimulation and/or the experiment at any point.

## 15.0 Risks to Subjects

### **tFUS Stimulation:**

When used at/below intensities deemed safe by the FDA, no significant and persisting side-effects have been reported, as confirmed in healthy volunteers(11), brain injury patients(7)as well as non-human primates(26).

In addition, although in the context of a different study, the FDA has granted to the device we will use a status of Category B (that is, safe and effective) Investigation Device Exemption (G130290), on 2/12/2014. Indeed, this is consistent with the known physics and biophysics of our stimulation protocol in which the device is operated at (acoustic) energy levels that are (1) well below those of a typical Pulsed Doppler ultrasound conventionally used in the clinical context in adults and children (by around 40%), and (2) within the energy limits deemed safe by the FDA.

### **Safety in case of pregnancy**

We do not know if the study drug will affect mother's milk or an unborn fetus. Therefore, breast-feeding and pregnant women are not allowed to take part in the study. If you are pregnant or become pregnant, there may be risks to the embryo or fetus that are unknown at this time. Women who can become pregnant must take a pregnancy test before the start of the study.

You should not father a child while on this study as the treatment may indirectly affect an unborn child. If you are sexually active and are at risk of causing a pregnancy, you and your female partner(s) must use a method to avoid pregnancy that works well or you must not have sex.

Unless you cannot have children because of surgery or other medical reasons, you must be using an effective form of birth control before you start the study. You must also agree to continue to use an effective form of birth control for 2 month/s after taking the study drug.

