Due to the inherent fundamentals of the waveform of ultrasonic forces, tFUS maximal energy can be focused both deep in the brain (2-12cm under the cap; for comparison, traditional TMS can stimulate 1-3.4cm^2 deep(14, 15)) and focally (as small as 0.5mm in diameter, and up to 1000mm; the facility of a standard, commercially-available 70mm figure-of-8 TMS coil is roughly 50mm^2 (14, 15)). Furthermore, tFUS has been demonstrated to safely stimulate neural tissue(12, 16-18), proposing cellular mechanisms for its efficacy(12, 18-23), and now is being used in human patients(24). Recently, tFUS administered to the thalamus of coma patients was demonstrated to assist in recovery of consciousness(24). Thus, tFUS is an extremely promising, new form of noninvasive deep brain stimulation that can be focused on deep brain structures to elicit meaningful behavioral responses. This proposal plans to use tFUS, administered to deep brain structures involved in reward and pain, to produce changes in brain functional connectivity.

We will be using the Brainsonix Low intensity focused ultrasound pulsation device. (BX Pulsar 1001). Please see the manufacturers description (Technical Summary) along with appendixes about the actual safety of the device itself.

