## 10.0 Study Design / Methods

- *Study Overview:* After determining eligibility and interest, written informed consent will be obtained from participants at the MUSC Center for Biomedical Imaging. Enrolled participants will be placed into the 3T MRI outfitted with a concurrent tFUS plus fMRI acquisition system (Brainsonix). First, participants will have baseline resting state functional neuroimaging conducted to quantify the functionally connected areas to the nucleus accumbens. Afterwards, while still in the MRI scanner, we will administer tFUS to the nucleus accumbens. Lastly, we conducted post-tFUS neuroimaging (same as pre-tFUS). This entire MRI procedure will take approximately 1 hour. Participants will be compensated \$100 for their time.
- *Recruitment, Screening, and Consent Procedures:* Healthy participants will be recruited from the MUSC community (students and staff) as well as general population from the greater Charleston region. We will recruit via flyers around campus, e-mail announcements and word of mouth. If interested in learning more about the study, potential subjects will be phone screened and educated regarding the study's details. If interested in participating in the study, they will be consented and enrolled into the study's protocol. We then will conduct a multi-panel urine drug screen to confirm they are not using illicit drugs and ask for their alcohol consumption (>3 drinks per day is exclusionary).
- *Pregnancy Test Procedures:* If participants are individuals biologically capable of becoming pregnant, they will be provided with a pregnancy test strip. After completing the pregnancy test, participants with negative results will be asked to continue to the remaining study procedures, whereas those with a positive result will be debriefed and released.
- *tFUS Procedures:* All tFUS will be administered in similar mythology to that in our prior published work (25). Within the MRI scanner, participants receive two, 10-min sessions of either active or sham tFUS spread 10 min apart targeting the nucleus accumbens [fundamental frequency: 650 kHz, Pulse repetition frequency: 10 Hz, Pulse Width: 5 ms, Duty Cycle: 5%, Sonication Duration: 30s, Inter-Sonation Interval: 30 s, Number of Sonifications: 10, ISPTA.0 995 mW/cm^2, ISPTA.3 719 mW/cm^2, Peak rarefactional pressure 0.72 MPa].

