- *Sham tFUS Procedures:* Participants will be randomized to receive either two, 10 minute active tFUS sessions, or two 10 minute sham tFUS sessions within the scanner. The sham sessions will include a transducer that is connected in a similar fashion to that of active tFUS, however the cable will not be plugged into the system, thus no ultrasound will be delivered to the participant. Participants will not know or be told whether they are receiving active- or sham- tFUS.
- *Neuroimaging Procedures:* All MRI imaging will be performed using a Siemens 3.0 T Prisma scanner equipped with a 32-channel head coil. MRI data will be acquired from all participants before and after tFUS administration. All MRI scan visits will be held at the MUSC Center for Biomedical Imaging (CBI; see the Facilities and Resources section). Each MRI scan session will include a high-resolution T1-weighted structural scan (whole brain sagittal acquisition, 224 slices, TR=2530ms,

TE=3.65ms, TI=1100ms, 1mm thick slices, FOV=256, 256x176, flip angle = 7 degrees.), followed by 24 minutes of resting-state scanning, then a concurrent tFUS/fMRI paradigm, and lastly, 24 more minutes of post-tFUS resting-state scanning. All functional scans will use the high-resolution fMRI protocol described in the Preliminary Study: whole brain acquisition, 136 axial slices, 1.5x1.5x1.5mm voxel size, TR=2000ms, TE=30ms, FOV=204mm, multi-band factor=3.

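### Does the pregnancy text, which speaks of a study drug and sets a birth-control condition absent from Section 5.0, require a change to the plan?

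*Protocol*

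**What the plan says.** The pregnancy subsection of Section 15.0 opens with "We do not know if the study drug will affect" breast milk or a fetus, and on that ground keeps pregnant and breast-feeding women out. It then addresses those who might cause a pregnancy: "You should not father a child while on this study", and those at risk of doing so "must use a method to avoid pregnancy that works well or you must not have sex". Its last paragraph sets a condition before entry, "Unless you cannot have children because of surgery or other medical reasons, you must be using an effective form of birth control before you start", and one afterwards: "You must also agree to continue to use an effective form of birth control for 2 month/s after taking the study drug".

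Elsewhere the intervention is a device throughout. Section 3.0 says "We will be using the Brainsonix Low intensity focused ultrasound pulsation device". Section 10.0 says "participants receive two, 10-min sessions of either active or sham tFUS" and "Participants will be randomized to receive either two, 10 minute active tFUS sessions, or two 10 minute sham tFUS sessions within the scanner". Section 18.0, Drugs or Devices, lists only the BX Pulsar 1001.

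Section 5.0 lists two inclusion criteria (age, and capacity to consent) and twelve exclusion criteria. One of the twelve excludes pregnant or lactating persons. None mentions birth control or fathering a child. Section 10.0 adds a pregnancy test: those who test positive are released, and those who test negative are asked to go on.

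**The concern.** Two things look wrong. First, the risk text names a product that nobody receives. Read literally, the lactation statement concerns that product, and the two-month term runs from an event that never happens, so it has no start date.

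Second, the birth-control requirement before entry reads like an eligibility condition, yet it is missing from the eligibility list. Someone who meets every item in Section 5.0 and has a negative pregnancy test could still fail a mandatory statement in Section 15.0, and staff might not know which section governs. At stake would be the accuracy of the information given to participants and the consistency of who is enrolled.

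**Working it through.** No arithmetic beyond counting applies, because the point depends on no error rate, effect size or sample size. The check is a comparison of texts.

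**1. Extent of the drug wording.** The term study drug occurs 2 times in the protocol, both in the pregnancy subsection. The number of drugs given is 0. Sections 3.0, 10.0 and 18.0 all describe a device. The slip is therefore real and confined to one subsection.

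**2. Whether the risk statement depends on the wrong word.** Only in part. The opening sentence ties lactation and fetal risk to the drug. A later sentence in the same paragraph warns of unknown risk to an embryo or fetus and names no product. The next paragraph attributes possible indirect harm to the treatment, which in this trial can only be the ultrasound. Fetal risk is thus also stated without the wrong word; the lactation statement alone rests on it.

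**3. Whether the two-month term can be dated.** Literally it cannot. If the word is read as meaning the trial's intervention (an assumption, but the only candidate in the protocol), the start is the visit itself. Section 1.0 describes a single visit, and Section 10.0 places both sessions in one scanning procedure of about an hour. Whichever session is taken as the start, the date is the same.

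**4. Eligibility list against the pregnancy text.** The count is 2 inclusion + 12 exclusion = 14 criteria, of which 1 concerns pregnancy or lactation and 0 concern birth control. The pregnancy text has 3 mandatory sentences about avoiding pregnancy. For a contradiction, Section 5.0 would have to admit people whom Section 15.0 bars. It is only silent, and both sections belong to the same protocol. The pregnancy-test step in Section 10.0 does not say that a negative result is the only condition for going on, so it does not contradict Section 15.0 either.

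**5. The fathering sentence against the two-month term.** One covers the time on study; the other adds a period before and a period after. They are cumulative, and a person can follow both.

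**6. What already agrees.** Exclusion for pregnancy appears in the Section 5.0 population text, its exclusion list and Section 15.0. Exclusion for lactation appears in the exclusion list and Section 15.0. The pregnancy test appears in Sections 10.0 and 15.0. No two of these conflict.

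**7. Reach into the statistics.** The primary outcome is resting-state connectivity before and after stimulation. Neither the drug wording nor the birth-control text enters its definition, its timing or the planned number of up to 10 participants.

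**The case for a change.** The strongest case for acting is that the words stand in the protocol's own risk section. That they were carried over from a template is an inference from the second-person style. A requirement to be using birth control before starting is hard to read as anything but an entry condition, and entry conditions belong in the eligibility list. Correcting the noun would cost one wording amendment. An analysis plan would not be expected to deal with any of this.

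Much of that stands. The noun is wrong, the lactation sentence depends on it, and the pre-study requirement is not in Section 5.0. What does not stand is the step from there to a defect in the plan. An undertaking about conduct can be obtained at consent without being repeated as a criterion; Section 9.0 has staff go through risks and benefits there, and the consent pages are not available to check. A participant is unlikely to think a drug was given when the procedures describe only ultrasound in a scanner. Reconciling the sections without saying whether the condition stays or goes would alter no result.

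**Conclusion.** This is a clerical slip, together with a silence in the eligibility list that the consent process may fill. It does not call for a change to the plan. Its size is two occurrences of a wrong noun in one subsection, and one pre-entry requirement not repeated among 14 criteria, in a single-visit study of up to 10 healthy adults. The number of participants affected is not given and is not estimated here. The effect on sample size, endpoint, analysis and conclusions is nil.

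The conclusion rests on two assumptions: that the drug term is read as the trial's only intervention, and that any birth-control undertaking is handled at consent, which the available text neither shows nor rules out. If the subsection is edited for other reasons, its wording and its fit with Section 5.0 are for the responsible clinician and the IRB to settle. Nothing here says which reproductive condition is right.

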### **Magnetic Resonance Imaging (MRI):**

MRI tests are non-invasive. There are no known risks or side effects associated with conventional MRI procedures except to those people who have electrically, magnetically or mechanically activated implants (such as cardiac pacemakers) or to those who have clips on blood vessels in their brain. There are no known additional risks for combined tFUS+fMRI procedures. However, an MRI may cause you to feel claustrophobic (uncomfortable in a small space) or anxious from the noises made by the machine.

**Unknown Risks:**

There is always the possibility of other risks for a relatively new technology. The Study team will let the participant know if they learn anything that might make the participant change their mind about participating in the study.

**Loss of Confidentiality:**

There is a risk of a loss of confidentiality of personal information. Subjects are informed that the information they provide, as well as participation in the study, will be kept strictly confidential, with access limited to the research staff. The identity of subjects in databases will be protected with alphanumeric codes. All data will be kept in locked file cabinets or on secure servers designed for use and access by Study Team members only.

## 16.0 Potential Benefits to Subjects or Others

There will be no direct benefit to the participant in the study. Data from this study, however, will benefit society by improving the understanding of if and how tFUS affects brain function and potentially work towards developing a novel therapeutic device.

## 17.0 Sharing of Results with Subjects

There is no plan to inform subjects of the results of the study, but they can always contact the research staff and ask. If there are significant new findings during the study, they will be notified.

## 18.0 Drugs or Devices

### Brainsonix BX Pulsar 1001 device.

The BX Pulsar device was initially tested at UCLA in epilepsy patients. This research required an FDA IDE, which I have attached to the IRB application. After this study was done and safety was established, the UCLA IRB now does not require an IDE and treats this form of ultrasound just like it does regular diagnostic ultrasound, which is non-significant risk. The diagnostic ultrasound devices and this one is the same in terms of what they can produce.

